## **10 Data analysis**

### **10.1 Sets for analysis**

This study is not designed based on statistical power, thus statistical tests will not be performed as p-values would not be reliable and will lead to misinterpretation of the data.

All analyses will be descriptive.

## **10.2 Patient demographics/other baseline characteristics**

Demographic and other baseline characteristics will be presented by treatment group. Continuous variables will be summarized by sample size, mean, standard deviation, median, minimum and maximum.

## **10.3 Analysis of the primary objective(s)**

### **10.3.1 Variable**

The primary objective is a feasibility assessment of the ability of the current Single-Site platform to perform major portions of the procedure prior to vascular division and extraction. This is a feasibility clinical study design to collect the primary evidence of safety and efficacy to support a marketing submission or application.

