## **4.0 Study design**

[figure not shown]
**Hypothesis:** We believe that the da Vinci system and its single port platform will offer solutions to the challenges of visualization, instrument articulation, and ergonomics that limit the widespread application of single-port donor nephrectomy as the preferred approach for renal donation.

**Methods:** We will perform an IRB-approved study of the use of the da Vinci Surgical System with Single-Site technology in donor nephrectomies. The IRB proposal and consent will be constructed to provide kidney donors with the opportunity to participate in our study. Patients will be informed of the potential risks and off-label use of the da Vinci Single-Site approach in our study. Because the standardized approach for renal donation at our center is single port donor nephrectomy, we anticipate enrollment of up to 20 patients for this study.

Patients will undergo robotic-assisted single-site nephrectomy performed by a two-surgeon team utilizing existing da Vinci instrumentation and Single Site platforms. Renal mobilization and vascular dissection will be performed with conversion to standardized laparoscopy for the final stages of vascular division with stapling devices and extraction. The primary objective is a feasibility measure of the ability of the current Single-Site platform to perform major portions of the procedure. Secondary objectives include operative times, blood loss, and surgeon ergonomics as measured via techniques developed in our surgical simulation center. Study cases will be compared to existing matched cohorts of single port donor nephrectomy cases performed by manual laparoscopy. The study population will include adults aged 18 to 70 of both genders who meet our center's criteria for renal donation and who consent to participate in the study. Our sample size of 20 patients is proposed to initiate this pilot study of the feasibility of robotic single port donor nephrectomy.

Statistical analysis will be performed on ergonomic and other collected data during the operative procedures and compared to matched patients. The proposed study of 20 patients may not generate statistically significant conclusions; however, we believe our observations will provide valid conclusions that support the use and continued development of robotic single port donor nephrectomy techniques.

Table 1 Study Design

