## **6.0 Treatments**

The study is a feasibility study. Patients will undergo a donor nephrectomy with the assistance of the investigational device, the da Vinci Surgical System with the Single-Site Instruments and Accessories.

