### **7.3 Efficacy**

The observations to assess efficacy of the investigational device include the proportion of the surgical procedure able to be performed with the device, prior to standard laparoscopic techniques that will be employed in the final surgical steps. Efficacy will be specifically measured in operative time, blood loss, and successful completion of donation. Post-operative assessments will include patient satisfaction and recovery surveys. The efficacy variables selected are standard for this indication/patient population.

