### **7.4 Safety**

Safety assessments include blood loss, intraoperative complications or injuries to adjacent structures, and successful completion of donation surgery. These will be

compared to center defined rates for these safety parameters. The safety assessments selected are standard for this indication/patient population.

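### Section 10.3.1 calls a descriptive, single-arm pilot of up to 20 patients the primary evidence for a marketing submission, and the plan gives no measure of uncertainty for its comparisons in 7.4 and 10.4.1

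*Combined protocol and SAP*

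**What the plan says.** On purpose, section 10.3.1 first restates a feasibility objective and then adds: "This is a feasibility clinical study design to collect the primary evidence of safety and efficacy to support a marketing submission or application". No other section mentions marketing. Section 6.0 says "The study is a feasibility study".

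On size, section 4.0 says "we anticipate enrollment of up to 20 patients for this study". Section 10.5 describes a pilot of 20 with no further calculation.

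On method, section 10.1 says the study was not designed on power, "thus statistical tests will not be performed as p-values would not be reliable and will lead to misinterpretation of the data", and then "All analyses will be descriptive".

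On comparisons, section 7.4 says "Safety assessments include blood loss, intraoperative complications or injuries to adjacent structures, and successful completion of donation surgery", and that these are to be "compared to center defined rates for these safety parameters". Section 10.4.1 sets operative time, blood loss and ergonomics against existing matched cohorts of manual single-port cases. Neither section names an estimate or an interval.

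On summaries, section 10.2 lists sample size, mean, standard deviation, median, minimum and maximum for baseline variables. Section 10.4.2 gives counts and percentages for adverse events, and means, medians, standard deviations and ranges for laboratory data.

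**The concern.** Two things do not fit together. The first is the role given to the data. A submission's primary evidence on safety and efficacy is normally expected to answer a stated question with stated precision, and this plan rightly says it was not built for that. The second is that the plan makes comparisons without showing how firm they are. When a count from at most 20 donors is set beside a center rate, no difference and too few patients to see a difference look the same unless an interval is shown.

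The participants are donors in good general health undergoing an off-label use of the device. A zero or low complication count is therefore the result most likely to be over-read, and the wording of 10.3.1 makes that easier.

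**Working it through.** **The plan's own figure.** The only design figure is the sample size of 20. No alpha, power, effect size, standard deviation, event rate or margin stands behind it, so it can be neither reproduced nor refuted. What can be computed is the precision that 20 patients give.

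**Inputs.** n = 20 is the ceiling (sections 4.0 and 10.5). Because section 4.0 says up to 20, n = 15 and n = 10 are shown as assumed shortfalls. The confidence level is assumed to be two-sided 95%, since the plan names none.

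**Zero events.** The exact (Clopper-Pearson) upper limit p solves (1 − p)^n = 0.025, so p = 1 − 0.025^(1/n).

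- n = 20: 1 − 0.831567 = 0.168433, or 16.8%
- n = 15: 1 − 0.781981 = 0.218019, or 21.8%
- n = 10: 1 − 0.691503 = 0.308497, or 30.8%

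**One event in 20.** The same method with beta quantiles gives 0.0013 to 0.2487, or 0.1% to 24.9%.

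**All donations completed.** The lower limit p solves p^n = 0.025. With n = 20, p = 0.025^(1/20) = 0.8316, so 20 of 20 is compatible with a true completion rate as low as 83.2%.

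**Where these limits apply.** They hold for outcomes that are yes or no for each patient, such as any complication or completed donation. They do not apply to the section 7.3 measure, "the proportion of the surgical procedure able to be performed with the device", which is a share of the operation within each patient, unless it is turned into a yes/no outcome per patient.

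**Matched comparison in 10.4.1.** The precision of a matched difference depends on the matching ratio and on the correlation within matched sets. The documents give neither, so no figure is offered.

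**Is an interval planned anywhere?** Sections 10.1 to 10.7 are all present in the supplied text and none specifies one; nor does section 7.4. The supplied text goes from 7.5.2 straight to 10, so this finding covers the text as supplied. Section 10.1 objects to tests and p-values. An interval is compatible with a descriptive analysis, so intervals are left out rather than ruled out.

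**The case against.** The strongest reply has four parts.

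- **The sentence in 10.3.1 itself says feasibility.** The sentence before it gives a feasibility objective, and no success criterion or decision rule depends on the marketing phrase. Primary may have been meant as first or preliminary. This stands as a limit on the point: it is one isolated sentence to correct. A reader might infer that the whole trial was built as a marketing study and is too small for that. The documents do not support this, because every other section describes a pilot.
- **The plan already admits its limits.** The synopsis and section 4.0 say that 20 patients may not give statistically significant results, and 10.1 says the study is unpowered. This is true, but an admission of low power does not tell a reader which complication rates remain possible.
- **Counts are reported with the percentages.** Anyone can therefore work out the limits for an adverse event. This also stands: for those summaries the information is not lost, only not displayed. It does not help with the matched differences in 10.4.1, where an outside reader could not rebuild the interval from group summaries if the analysis must respect the matching.
- **The testing rules do not flatly contradict each other.** A reader might set the statement in 10.1 that no tests will be done against the sentence in 10.4.2 on exploratory tests. The latter is conditional: it limits how any tests that happen to be run may be used. That is a loose end in wording, and so is the promise of statistical analysis against matched patients in the synopsis and section 4.0.

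**Conclusion.** The point holds as a mismatch between one stated purpose and the design, together with a missing measure of uncertainty for comparisons that the plan commits to. It should be fixed, and the fix is small.

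The size rests on exact two-sided 95% limits for outcomes that are binary per patient. At full enrollment, no observed event is compatible with a true rate up to 16.8%, and complete success with a true completion rate down to 83.2%. That is useful for feasibility and weak as primary evidence of safety.

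Three stronger readings are not supported. First, small size is not a fault in a declared pilot, and no power calculation or larger sample is called for. Second, nothing in the plan says that a zero count will be presented as proof of safety; the wording only leaves room for it. Third, a reader might want to state the chance that the study would miss a given rise over the center rate. The documents do not give the center rates, so any such figure would rest on assumed rates, and it would be a power calculation in a plan that declines to test.

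**What to change.** 1. **Section 10.3.1.** Change the description of what is collected to *preliminary evidence of feasibility, safety and efficacy*, and do not present the study as sufficient for marketing. Efficacy stays in the sentence because 7.3 and 10.4.1 keep efficacy assessments.
2. **Sections 10.4.2 and 7.4.** Report binary safety outcomes, including completion of donation, as n/N, percentage and exact (Clopper-Pearson) two-sided 95% interval, beside the center rate. Give that rate's own n/N, since it is itself an estimate from a finite series.
3. **Section 10.4.1.** Report differences from the matched cohort with 95% intervals by a method that respects the matching: paired differences if matching is 1:1, a matched-set model otherwise. The matching ratio must be written down first.
4. **Section 10.5.** State the precision: 0 of 20 leaves rates up to 16.8% not excluded, and more if fewer enroll.
5. **Minor.** Align 10.1 with 10.4.2, either by deleting the exploratory-test sentence or by allowing tests labelled exploratory, with all that are run reported.

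The cost is a few changed sentences and some extra table columns. No patients or assessments are added. The stated claim becomes more modest.

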## **10.4 Analysis of secondary objectives**

### **10.4.1 Efficacy (secondary)**

Secondary objectives include operative times, blood loss, and surgeon ergonomics as measured via techniques developed in our surgical simulation center. Study cases will be compared to existing matched cohorts of single port donor nephrectomy cases performed by manual laparoscopy.

### **10.4.2 Safety**

Safety variables to be assessed include discontinuation from study, discontinuation from treatment, renal function, AE/infection, SAE, notable events, laboratory tests, and vital signs.

Adverse events will be summarized by presenting, for each treatment group, the number and percentage of patients having any adverse event, having an adverse event in each organ system and having each individual adverse event. The same type of summaries will be provided for serious adverse events and for events suspected to be related to the study device. Any other information collected (e.g. severity or relatedness to study device) will be listed as appropriate.

Laboratory data will be summarized by baseline values to most extreme post-baseline values, by presenting summary statistics of raw data and change from baseline values (means, medians, standard deviations, ranges) and by the flagging of notable values in data listings.

Data from other tests (e.g. vital signs) will be listed, notable values will be flagged, and any other information collected will be listed as appropriate. Any statistical tests performed to explore the data will be used only to highlight any interesting comparisons that may warrant further consideration.

The data collected will be presented in listings, summary tables and graphs.

### **10.4.3 Resource utilization**

Data related to Resource Utilization will be used for the purpose of economic evaluation which will be analyzed in a separate report.

#### **10.4.4 Health-related Quality of Life**

The change from baseline in the profile and summary scores of the SF-36 will be assessed in the treatment group.

#### **10.5 Sample size calculation**

This study is a pilot study of 20 patients without additional sample size calculation.

#### **10.6 Power for analysis of critical secondary variables**

Not applicable.

#### **10.7 Interim analysis**

Routine follow-up appointments will occur 2 weeks and 6 months after operation.
